7.3.11 Adverse Events

The investigator or site staff will be responsible for detecting, documenting and reporting events that meet the definition of an AE or SAE.

7.3.12 Definition of AE

Any untoward medical occurrence in a patient or clinical investigation subject, temporally associated with the use of a medicinal product, whether or not considered related to the medicinal product.

Note: An AE can therefore be any unfavorable and unintended sign (including an abnormal laboratory finding), symptom, or disease (new or exacerbated) temporally associated with the use of a medicinal product. For marketed medicinal products, this also includes failure to produce expected benefits (i.e., lack of efficacy), abuse or misuse.

Events meeting the definition of an AE include:

- Exacerbation of a chronic or intermittent pre-existing condition including either an increase in frequency and/or intensity of the condition
- New conditions detected or diagnosed after study treatment administration even though it may have been present prior to the start of the study
- Signs, symptoms, or the clinical sequelae of a suspected interaction
- Signs, symptoms, or the clinical sequelae of a suspected overdose of either study treatment or a concomitant medication (overdose per se will not be reported as an AE/SAE).

“Lack of efficacy” or “failure of expected pharmacological action” per se will not be reported as an AE or SAE. However, the signs and symptoms and/or clinical sequelae resulting from lack of efficacy will be reported if they fulfil the definition of an AE or SAE.

Events that **do not** meet the definition of an AE include:

- Medical or surgical procedure (e.g., endoscopy, appendectomy); the condition that leads to the procedure is an AE
- Situations where an untoward medical occurrence did not occur (social and/or convenience admission to a hospital)
- Anticipated day-to-day fluctuations of pre-existing disease(s) or condition(s) present or detected at the start of the study that do not worsen
- The disease/disorder being studied, or expected progression, signs, or symptoms of the disease/disorder being studied, unless more severe than expected for the subject's condition

AEs which meet all of the following criteria:

- Serious
- Unexpected (as per assessment according to safety information in Investigator Brochure)
- There is at least a reasonable possibility that there is a causal relationship between the event and the medicinal product

will be classified as Suspected Unexpected Serious Adverse Reactions (**SUSARs**) and should be reported to the relevant ethics committee and to the relevant Health Authorities in accordance with applicable regulatory requirements for expedited reporting. Sponsor/designated CRO will report SUSARs to the ethics committee and relevant health authorities.

7.3.13 Definition of SAE

A serious adverse event is any untoward medical occurrence that, at any dose:

- a. Results in death
- b. Is life-threatening

NOTE: The term 'life-threatening' in the definition of 'serious' refers to an event in which the subject was at risk of death at the time of the event. It does not refer to an event, which hypothetically might have caused death, if it were more severe.

- c. Requires hospitalization or prolongation of existing hospitalization

NOTE: In general, hospitalization signifies that the subject has been detained (usually involving at least an overnight stay) at the hospital or emergency ward for observation and/or treatment that would not have been appropriate in the physician's office or out-patient setting. Complications that occur during hospitalization are AEs. If a complication prolongs hospitalization or fulfills any other serious criteria, the event is serious. When in doubt as to whether "hospitalization" occurred or was necessary, the AE should be considered serious.

Hospitalization for elective treatment of a pre-existing condition that did not worsen from baseline is not considered an AE.

d. Results in disability/incapacity, or

NOTE: The term disability means a substantial disruption of a person's ability to conduct normal life functions. This definition is not intended to include experiences of relatively minor medical significance such as uncomplicated headache, nausea, vomiting, diarrhea, influenza, and accidental trauma (e.g. sprained ankle) which may interfere or prevent everyday life functions but do not constitute a substantial disruption.

e. Is a congenital anomaly/birth defect

f. Medical or scientific judgement should be exercised in deciding whether reporting is appropriate in other situations, such as important medical events that may not be immediately life-threatening or result in death or hospitalization but may jeopardize the subject or may require medical or surgical intervention to prevent one of the other outcomes listed in the above definition. These should also be considered serious. Examples of such events are invasive or malignant cancers, intensive treatment in an emergency room or at home for allergic bronchospasm, blood dyscrasias or convulsions that do not result in hospitalization, or development of drug dependency or drug abuse.

g. All events of possible drug-induced liver injury with hyperbilirubinaemia defined as ALT³ 3xULN **and** bilirubin³ 2xULN (>35% direct) (or ALT³ 3xULN and INR>1.5, if INR measured) termed 'Hy's Law' events (INR measurement is not required and the threshold value stated will not apply to patients receiving anticoagulants).

NOTE: bilirubin fractionation is performed if testing is available. If testing is unavailable, record presence of detectable urinary bilirubin on dipstick indicating direct bilirubin elevations and suggesting liver injury. If testing is unavailable and a subject meets the criterion of total bilirubin³ 2xULN, then the event is still reported as an SAE. If INR is obtained, include values on the SAE form. INR elevations >1.5 suggest severe liver injury.

7.3.14 AE and SAE reporting requirement and timeline

The investigator or site staff is responsible for detecting, documenting and reporting events that meet the definition of an AE or SAE. AEs will be collected from the start of study treatment (Visit 2) and until the follow up contact. SAEs will be collected from the time a subject consent to participate in the study up to and including any follow up contact.

All SAEs will be reported to Reistone Biopharma/designated CRO within 24 hours. Prompt notification of SAEs by the investigator to Reistone Biopharma/designated CRO is essential so that legal obligations and ethical responsibilities towards the safety of subjects are met. All SAEs will be followed up until resolution, until the condition stabilizes, until the event is otherwise explained, or until the subject is lost to follow-up. Once resolved, the SAE eCRF page will be updated. The investigator should report SAE/serious incident per local regulations and local EC requirement. The investigator will ensure that follow-up includes any supplemental investigations as may be indicated to elucidate the nature and/or causality of the SAE. This may include additional laboratory tests or investigations, histopathological examinations, or consultation with other health care professionals.

Reistone Biopharma/designated CRO has a legal responsibility to notify both the local regulatory authority and other regulatory agencies about the safety of a product under clinical investigation according to local regulations. Reistone Biopharma/designated CRO will comply with country specific regulatory requirements relating to safety reporting to the regulatory authority, Institutional Review Board (IRB)/Independent Ethics Committee (IEC) and investigators.

Investigator safety reports are prepared for suspected unexpected serious adverse reactions according to local regulatory requirements and Reistone Biopharma/designated CRO policy and are forwarded to investigators as necessary.

An investigator who receives an investigator safety report describing a SAE(s) or other specific safety information (e.g., summary or listing of SAEs) from Reistone Biopharma/designated CRO will file it with the IB and will notify the IRB/IEC, if appropriate according to local requirements.

7.3.15 Adverse Event of Special Interest (AESI)

The AE of special interest (AESI) (serious or non-serious) are determined based on previous knowledge about the disease and the mechanism of action of the investigational drug, as well as safety information from a similar class of drug. AESI is one of scientific and medical concern specific to the product or program, for which ongoing monitoring and rapid communication by the investigator to the sponsor may be appropriate. Such events require heightened surveillance and further investigation in order to characterize and understand them. The AESI will be managed and follow-up according to the SAE timeline and procedure. The study's AESI includes.

- Serious infection: Serious infection is defined as any infection (viral, bacterial, and fungal) requiring hospitalization or parenteral antimicrobials for more than 3 days.
- Thromboembolic event: Thromboembolic events are divided into two major groups which are venous thromboembolic events, including deep vein thrombosis (DVT) and pulmonary embolism (PE), and arterial thromboembolic events, including arterial thrombosis and cerebrovascular accident (CVA).

7.4 Pharmacokinetics

Figure 1 consists of three vertically stacked panels, each containing a 2x2 grid of plots. The top panel shows a 2x2 grid of plots. The left column shows the effect on the mean (black) and variance (white) of the number of individuals in the population. The right column shows the effect on the mean (black) and variance (white) of the number of individuals in the population. The middle panel shows a 2x3 grid of plots. The left column shows the effect on the mean (black) and variance (white) of the number of individuals in the population. The middle column shows the effect on the mean (black) and variance (white) of the number of individuals in the population. The bottom panel shows a 2x3 grid of plots. The left column shows the effect on the mean (black) and variance (white) of the number of individuals in the population. The middle column shows the effect on the mean (black) and variance (white) of the number of individuals in the population. The right column shows the effect on the mean (black) and variance (white) of the number of individuals in the population.

8. Data Management

For this study subject data will be entered into Reistone Biopharma/designated CRO defined electronic case report forms (eCRFs), transmitted electronically to Reistone Biopharma /designated CRO and combined with data provided from other sources in a validated data system. Management of clinical data will be performed in accordance with applicable Reistone Biopharma/designated CRO data review, verification and cleaning procedures to ensure the integrity of the data, e.g., removing errors and inconsistencies in the data. Adverse events and concomitant medications terms will be coded using MedDRA. An appropriate medical dictionary that covers all approved drugs in the region will be referenced. eCRFs (including queries and audit trails) will be retained by Reistone Biopharma/designated CRO, and copies will be sent to the investigator to maintain as the investigator copy. In all cases, subject initials will not be collected or transmitted to Reistone Biopharma/designated CRO.

9. Data Analysis and Statistical Considerations

9.1 Hypothesis

The primary objective of the study will be evaluated for SHR0302 dose groups (8mg QD, 4mg BD, 4mg QD) compared to placebo group with respect to the percentage of patients with clinical response at week 8.

The Hochberg method will be used to maintain the 2-sided study-wise Type I error rate at 0.1. The null and alternative hypothesis for the primary endpoint that will be tested are:

H_{01} : The percentage of patients with clinical response at week 8 in SHR0302 8mg group – the percentage of patients with clinical response at week 8 in placebo group = 0;

H_{11} : The percentage of patients with clinical response at week 8 in SHR0302 8mg group – the percentage of patients with clinical response at week 8 in placebo group $\neq 0$.

H_{02} : The percentage of patients with clinical response at week 8 in SHR0302 4mg BD group – the percentage of patients with clinical response at week 8 in placebo group = 0;

H_{12} : The percentage of patients with clinical response at week 8 in SHR0302 4mg BD group – the percentage of patients with clinical response at week 8 in placebo group $\neq 0$.

H_{03} : The percentage of patients with clinical response at week 8 in SHR0302 4mg QD group – the percentage of patients with clinical response at week 8 in placebo group = 0;

H_{13} : The percentage of patients with clinical response at week 8 in SHR0302 4mg QD group – the percentage of patients with clinical response at week 8 in placebo group $\neq 0$.

Two-sided p-values for the treatment group differences will be provided for all comparisons by using CMH test. Thus, 3 p-values will be gained and start with the least significant comparison and continue as long as tests are not significant until the first time when a significant comparison occurs and all remaining hypotheses will be rejected. Order the three p values as $(p_{(3)}, p_{(2)}, p_{(1)})$, where $p_{(3)} \geq p_{(2)} \geq p_{(1)}$. The decision rules are provided in below figure ([Figure 2](#)).

[figure not shown]

Figure 2. The decision rules of hypothesis

9.2 Study Design Considerations

9.2.1 Sample Size Assumptions

The sample size calculation is based on pairwise comparison of clinical response at week 8 among SHR0302 8mg, 4mg QD, 4mg BD dose group and placebo group at the 2-sided 0.1 significance level. 57%, 57%, 50%, 30% clinical response are assumed for 8mg QD, 4mg BD and 4mg QD dose group, placebo group at week 8 respectively. The planned sample size of 35 evaluable subjects per treatment group will provide 80% global power to detect at least 1 dose

group is different from placebo group by using Hochberg's step up test. The total sample size is 152 randomized subjects with consideration of 8% drop out rate.

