5.1 Number of subjects

152 eligible subjects will be randomized to achieve an estimated 140 evaluable subjects in the study. The following eligibility criteria are designed to select subjects for whom protocol treatment is considered appropriate. All relevant medical and non-medical conditions should be taken into consideration when deciding whether a particular subject is suitable to participate in this study. Subject eligibility should be reviewed and documented by an appropriately qualified member of the investigator's study team before subjects are included in the study. Subject must be able to provide an informed consent to participate in this study at his own will.

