9.3.4.3 Efficacy Analysis

Analysis of the Primary Efficacy Endpoint

The primary analysis will be based on the FAS population. In addition, an analysis of the PPS population will be used to support the primary efficacy analysis.

For clinical response at week 8, the comparisons of the percentage of subjects achieving clinical response in each treatment versus placebo will be made using a stratified Cochran-Mantel-Haenszel (CMH) test with stratification according to prior anti- TNF α /biological treatment (with or without). Missing data will be imputed as Non-completers considered failure (NCF).

Sensitivity analyses for the primary endpoint include: (1) the same analysis using the per-protocol analysis set (2) using last-observation-carried-forward (LOCF) imputation for subscore other than endoscopy of Mayo score.

Analysis of the Secondary Efficacy Endpoints

Dichotomized secondary efficacy endpoints listed below will be analyzed by using a CMH Chi-Square test with stratification according to prior anti- TNF α treatment (with or without). Missing data will be imputed as Non-completers considered failure (NCF).

- ✓ The percentage of subjects with clinical remission (per 9-point modified Mayo score) at week 8
- ✓ The percentage of subjects with clinical remission (per total Mayo score) at week 8
- ✓ The percentage of subjects achieve endoscopic remission at week 8

The continuous secondary endpoints listed below will be analyzed using an analysis of covariance (ANCOVA) model including treatment group, baseline value, with/without previous exposure to anti-TNF α treatment as main effects. Missing data will be imputed by using Last-observation-carried-forward (LOCF) approach for subscore other than endoscopy of Mayo score.

- ✓ Change from baseline in 9-point modified Mayo score at week 8
- ✓ Change from baseline in total Mayo score at week 8
- ✓ Changes from baseline in partial Mayo score (Mayo score without endoscopy) at week 1, 4, 8, 9, 12 and 16.
- ✓ Change from baseline in the level of biomarkers CRP, fecal calprotectin.

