The efficacy, safety, tolerability, and anti-inflammatory data generated by this proposed phase II study will be essential for evaluating the potential of this promising, novel anti-inflammatory agent as a treatment for moderate to severe active ulcerative colitis so that one or two doses can be selected to progress into further clinical development.

Figure 1: Study Design Diagram

---

Document:

\\\ieedc-vnasc01\Biosdata\Reistone\SHR0302\CZA55021\Biostatistics

Author:

[REDACTED]

Version Number:

[figure not shown]
Final v1.2

Version Date:

23Mar2021

Template No: CS\_TP\_BS016 Revision 5  
Effective Date: 01Apr2018

Reference: CS\_WI\_BS005

The sample size calculation is based on pairwise comparison of clinical response at week 8 among SHR0302 8mg, 4mg BD, 4mg QD dose group and placebo group at the 2-sided 0.1 significance level. 57%, 57%, 50%, 30% clinical response are assumed for 8mg QD, 4mg BD and 4mg QD dose group, placebo group at week 8 respectively. The planned sample size of 35 evaluable patients per treatment group will provide 80% global power to detect at least 1 dose group is different from placebo group by using Hochberg's step-p test. The total sample size is 152 randomized patients with consideration of 8% drop out rate. 152 eligible patients will be randomized to achieve an estimated 140 evaluable patients in the study.

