For clinical response at week 8, the comparisons of the percentage of patients achieving clinical response in each treatment versus placebo will be made using a stratified Cochran-Mantel-Haenszel (CMH) test with stratification according to prior anti-TNF $\alpha$ /biological treatment (with or without). The CMH method is a technique that generates an estimate after adjusting for or taking into account stratification. Strata-adjusted proportion difference between each SHR0302 dose group and placebo group will be obtained by CMH method [1].

Missing data will be imputed as NCF. If a patient is missing one or more Mayo subscores at the visit where the endpoint is being assessed, the patient would be considered a treatment failure.

Two-sided p-values for the treatment group differences will be provided for all comparisons. Thus, 3 p-values will be gained. Order the three p values as  $(p_{(3)}, p_{(2)}, p_{(1)})$ , where  $p_{(3)} \geq p_{(2)} \geq p_{(1)}$ . The decision rules are provided in Figure 2. Note that in Figure 2,  $H_{(01)}$  is the

corresponding null hypothesis of the smallest p value  $p_{(1)}$ ,  $H_{(02)}$  is the corresponding null hypothesis of the second smallest p value  $p_{(2)}$ , and  $H_{(03)}$  is the corresponding null hypothesis of the largest p value  $p_{(3)}$ . Therefore,  $H_{(01)}$  and  $H_{01}$  may not be the same null hypothesis,  $H_{(02)}$  and  $H_{02}$  may not be the same null hypothesis,  $H_{(03)}$  and  $H_{03}$  may not be the same null hypothesis, either.

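### The 80% global power is worked out on 35 evaluable patients per arm, but the primary analysis counts dropouts as failures; on the plan's own figures it has about 74%

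*Protocol*

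**What the plan says.** Protocol 9.2.1 gives the response rates: "57%, 57%, 50%, 30% clinical response are assumed for 8mg QD, 4mg BD and 4mg QD dose group, placebo group at week 8". It attaches power to a number of evaluable patients: "The planned sample size of 35 evaluable subjects per treatment group will provide 80% global power to detect at least 1 dose" group to differ from placebo. It then inflates for dropout: "The total sample size is 152 randomized subjects with consideration of 8% drop out rate". Protocol 5.1 confirms the intent: "152 eligible subjects will be randomized to achieve an estimated 140 evaluable subjects in the study". SAP 3.1 carries the same statement: "The planned sample size of 35 evaluable patients per treatment group will provide 80% global power".

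The multiplicity rule is in Protocol 9.1: "The Hochberg method will be used to maintain the 2-sided study-wise Type I error rate at 0.1".

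The primary analysis (Protocol 9.3.4.3, SAP 15.1.1) is a CMH test on the full analysis set (FAS), stratified by prior biologic exposure. The FAS (Protocol 9.3.1, SAP 5.3) requires a dose of study drug and one valid Mayo-related score, but no week 8 result. SAP 15.1.1 states: "Missing data will be imputed as NCF", that is, non-completers considered failure, and a patient lacking any Mayo subscore at the assessment is a treatment failure. Protocol 9.3.4.3 has the same rule.

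**The concern.** The sample-size section and the analysis section treat a dropout in opposite ways. The first lets 3 of 38 patients per arm disappear and applies the full response rates to the other 35. The second keeps all 38 and scores those 3 as non-responders. Scoring the same fraction of every arm as failures shrinks every difference from placebo by that fraction, and the three extra patients per arm have to make up for it.

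If they do not, the quoted power belongs to an analysis that will not be run. SAP 3.1 says the trial is meant to select one or two doses for further development. Anyone reading a null result would rely on this figure to judge how likely it was that a real effect was missed.

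**Working it through.** **Inputs.** Rates 57/57/50/30%, 35 evaluable per arm, 152 randomised, 8% dropout, 80% power (Protocol 9.2.1); 140 evaluable (Protocol 5.1); Hochberg over three comparisons at two-sided 0.1 (Protocol 9.1); equal allocation (Protocol 1.3). The share of biologic-exposed patients is not given, so I varied it from 10% to 50%.

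**Dropout arithmetic.** 152/4 = 38 and 140/4 = 35 per arm. 12/152 = 7.9%, and 140/0.92 = 152.2, so the 152 is consistent with 8%.

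**Do dropouts stay in the primary analysis?** Yes. SAP 3.3 removes patients without week 8 results from the per-protocol set only, in order to have an analysis free of failure imputation. Eligibility needs a baseline Mayo score, so few dosed patients can fail the FAS requirement.

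**Method.** Simulate four binomial arms with a shared placebo (200,000 to 400,000 trials per setting). Compute three two-sided p-values, ordered p(1) ≤ p(2) ≤ p(3). Count a success if p(3) ≤ 0.1, or p(2) ≤ 0.05, or p(1) ≤ 0.0333. Tests are without continuity correction.

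**The plan's own figure.** At 35 per arm and 57/57/50/30%, the pooled chi-square test gives 80.1%. The stated 80% reproduces.

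**The planned analysis.** Multiply each rate by 0.92:
- 57% becomes 52.4%, 50% becomes 46.0%, 30% becomes 27.6%.
- The larger difference falls from 27 to 24.8 points, the smaller from 20 to 18.4.

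| Setting | Pooled chi-square | Stratified CMH | Smooth normal approximation (pooled) |
|---|---|---|---|
| 35 per arm, full rates | 80.1% | 78.1–78.8% | 77.7% |
| 38 per arm, rates × 0.92 | 73.5% | 73.6% | 75.8% |
| 38 per arm, full rates | 79.1% | 79.1–79.3% | 80.9% |

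At 38 per arm, 4% dropout gives about 76% and 12% about 71% (pooled chi-square).

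**Hand check of direction.** Take z = difference / √(2p̄(1−p̄)/n), with p̄ the mean of the two rates.
- 57% v 30%, n = 35: 0.27/√(2 × 0.435 × 0.565/35) = 0.27/0.1185 = 2.28.
- 52.4% v 27.6%, n = 38: 0.2484/√(2 × 0.400 × 0.600/38) = 0.2484/0.1124 = 2.21.
- 50% v 30%, n = 35: 0.20/√(2 × 0.40 × 0.60/35) = 0.20/0.1171 = 1.71.
- 46% v 27.6%, n = 38: 0.184/√(2 × 0.368 × 0.632/38) = 0.184/0.1106 = 1.66.

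Each expected z falls by about 3%, so the extra patients do not make up the loss.

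**What would restore 80%.** With failures counted and the pooled chi-square test, 42 per arm (168 in all) gives 80.2%.

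**The case against.** Four points deserve an answer.

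1. *The rates may already count dropouts as failures.* The plan does not say which kind they are. On that reading 38 per arm gives about 79%, and the gap largely closes. This stands as a genuine ambiguity. But the plan pairs the rates with evaluable patients, and on the other reading 35 is the wrong n and the dropout inflation has no purpose. The section needs correcting either way.

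2. *Part of the drop is discreteness.* This stands. With full rates, simulated pooled chi-square power runs 80.1%, 79.5%, 77.9%, 79.1% at n = 35, 36, 37, 38, so the published figure sits on a local peak. The smooth pooled approximation loses only about 2 points. For the stratified CMH test the like-for-like loss is 4.5 to 5 points. The level at 38 per arm is unaffected: the planned test has about 74%.

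3. *Dropout may differ by arm, or occur mainly in non-responders.* An overall 8% split as 6.7% on active arms and 12% on placebo gives about 80%, because the larger difference becomes 57 × 0.933 − 30 × 0.88 = 26.8 points. A split the other way hurts: 9.3% active and 4% placebo gives 57 × 0.907 − 30 × 0.96 = 22.9 points. The plan gives no unequal split, and 35 evaluable of 38 in every group implies an equal one. If dropouts would mostly not have responded anyway, the dilution is smaller. Both assumptions should be stated.

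4. *Some dropouts may fall outside the FAS.* With 37 per arm in the FAS power is about 74.5%, with 36 about 77.9%. Neither reaches 80%.

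**Conclusion.** The concern holds. The stated 80% is correct for 35 evaluable patients per arm, but that is not the primary analysis. With 38 per arm and 8% counted as failures, global power is about 74% (73.5–73.8% across the pooled and stratified tests; about 76% on a smooth pooled approximation). The chance of declaring no dose effective is then about 26% rather than 20%.

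This rests on four assumptions: the rates apply to evaluable patients; dropout is 8% and equal across arms; it is unrelated to response; and essentially all dropouts are in the FAS. If the rates already include dropouts as failures, power is about 79% and the fault lies in how the basis is described. The analysis method and type I error control are unaffected.

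**What to change.** In Protocol 9.2.1 and SAP 3.1, state whether 57/57/50/30% are rates among evaluable patients or rates over all randomised patients with non-completers as failures. Then give power for the analysis that will be run.

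- *If evaluable rates:* With 38 randomised per arm and 8% non-completers counted as failures, dropout taken as equal across arms and unrelated to response and all dropouts in the FAS, global power is about 74% (Hochberg, two-sided 0.1).
- *If failure-imputed rates:* State that, give power at 38 per arm (about 79% with the planned test), and remove the evaluable basis and the dropout inflation.

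Name the test and the method of calculation, since the figure moves by a few points between them. The cost is wording and a slightly less favourable stated power. No patients, procedures or analyses change.
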